7.2.3 Definition of serious adverse event

A serious adverse event (SAE) refers to a medical occurrence during the clinical study that results in hospitalization, prolonged hospitalization, disability, incapacity, life-threatening or death, or congenital malformation. The following medical events are included:

- Events resulting in death;
- Life-threatening events (defined as when the subject is at immediate risk of death at the time of the event);
- Events resulting in hospitalization or prolonged hospitalization;
- Events resulting in permanent or serious disability/incapacity/impairment of work ability;
- Congenital anomalies or birth defects;
- Other important medical events (defined as events that may jeopardize the subject or require interventions to prevent any of the above).

During the study, AEs resulting in hospitalization or prolonged hospitalization should be considered SAEs. Hospitalization does not include the following:

- ✓ Hospitalization at a rehabilitation institution
- ✓ Hospitalization at a sanatorium
- ✓ General emergency admission
- ✓ Day surgery (e.g., outpatient/same-day/ambulatory surgery)
- ✓ Social reasons (medical insurance reimbursement, etc.)

Hospitalization or prolonged hospitalization not related to the worsening of AEs is not considered an SAE. For example:

- ✓ Hospitalization due to the pre-existing disease without new AEs and aggravation of the pre-existing disease (e.g., hospitalization to examine laboratory abnormalities that have persisted from before the study until now);
- ✓ Hospitalization for management reasons (e.g., annual physical examination);
- ✓ Hospitalization during the study as specified in the study protocol (e.g., as required by the protocol);
- ✓ Elective hospitalization unrelated to worsening of AEs (e.g., elective surgery);
- ✓ Scheduled treatment or surgery that should be documented throughout the entire study protocol and/or in the subjects' individual baseline information;
- ✓ Hospitalization merely for use of blood products.

Diagnostic or therapeutic invasive (e.g., surgery) and non-invasive procedures should not be reported as AEs. However, when a condition resulting in such procedures meets the definition of an AE, it should be reported as so. For example, acute appendicitis during the AE reporting period should be reported as an AE, and the resulting appendectomy shall be recorded as the treatment of the AE.

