2.2 Study Endpoints

Primary endpoint:

- Objective response rate (ORR).

Secondary endpoints:

- Progression free survival (PFS);
- Duration of response (DoR);
- Disease control rate (DCR);
- Incidence and severity of adverse events (AEs) and serious adverse events (SAEs), vital signs, ECG, and laboratory abnormalities.

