5.5.4 Hematopoietic growth factor and blood transfusion

Any granulocyte colony-stimulating factor, erythropoietin, thrombopoietin, and other hematopoietic stimulation factors, as well as blood transfusion and blood products (eg., albumin) are prohibited as primary prophylaxis before treatment. However, these treatments are allowed for treating AEs.

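### The SAE definition excludes an undefined category of emergency admission from hospitalization, so AEs that lead to emergency inpatient stays may be classified inconsistently and under-counted

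*Protocol*

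**What the plan says.** Three parts of protocol section 7.2.3 bear on this point.

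- **The rule.** "During the study, AEs resulting in hospitalization or prolonged hospitalization should be considered SAEs".
- **A first list, with no condition attached.** It opens with "Hospitalization does not include the following" and has five items: rehabilitation institutions, sanatoria, "General emergency admission", day surgery and social reasons. Day surgery and social reasons carry explanatory examples in brackets. The emergency item has none.
- **A second list, with a condition.** It opens with "Hospitalization or prolonged hospitalization not related to the worsening of AEs is not considered an SAE". Its examples include pre-existing disease, elective stays and "Hospitalization merely for use of blood products".

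The section's other routes to seriousness are death, immediate risk of death, permanent or serious disability, congenital anomaly and other important medical events. Neither list alters them.

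Section 2.2 names this secondary endpoint: "Incidence and severity of adverse events (AEs) and serious adverse events (SAEs), vital signs, ECG, and laboratory abnormalities". Section 7.4.3 requires an SAE to reach the authorities, the sponsor and the ethics committee within 24 hours of awareness. SAP section 11.4.1 tabulates SAEs and gives no definition of its own.

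**The concern.** Emergency admission is an ordinary way for an acute toxicity to reach an inpatient bed. The documents themselves name one event that can present like this. Upper gastrointestinal hemorrhage is described in section 1.1.2 as the common serious adverse drug reaction in both groups of the apatinib phase III study. The summary of changes for protocol version 6.0 also lists it among 4 apatinib-related SAEs in 11 patients given the combination.

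An exclusion worded by route of entry, and not by whether the subject stayed in hospital, sits badly beside a rule that makes AE-driven hospitalization serious. Three things depend on the classification:

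- **Expedited reporting.** The 24-hour report to authorities and ethics committee follows from SAE status.
- **Length of collection.** In Table 14 (section 7.4.1), treatment-related SAEs are collected without time limit, while treatment-related non-serious AEs are collected only to the end of safety follow-up. A late related event read as non-serious might not be recorded.
- **The secondary endpoint.** The SAP uses the site's classification as it stands. Section 8 of the protocol pools all centers, so differences in reading between sites would not show in the tables.

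**Working it through.** No arithmetic applies. The plan states no SAE rate or emergency-admission rate, so there is no figure to reproduce. The check is a reading of the text.

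**Step 1: does a condition limit the emergency item?** The only limit to stays unrelated to worsening AEs is in the lead-in to the second list. The emergency item is in the first list, whose lead-in is unconditional. The limit does not reach it.

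**Step 2: is the phrase defined elsewhere?** Protocol sections 7.2.2, 7.2.4, 7.3 and 7.4 and SAP section 11.4.1 neither define it, nor confine it to attendance without an inpatient stay, nor say that an AE-driven emergency admission still counts.

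**Step 3: apply both available readings to one event.** Take an AE that brings a subject in as an emergency, followed by an inpatient stay, with no immediate risk of death.

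| Reading of the item | Hospitalization criterion | Result |
|---|---|---|
| Literal: emergency admissions are not hospitalization | Not met | SAE only if judged an important medical event or caught by another criterion |
| Narrow: only an emergency-room visit is meant | Met by the inpatient stay | SAE |

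The same event can therefore be serious at one site and non-serious at another, and each site can point to the text.

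**Step 4: do other provisions close the gap?** They close part of it.

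- The life-threatening criterion needs immediate risk of death. The important-medical-event criterion depends on judgment. Hospitalization is the more objective test.
- Potential drug-induced liver injury must be reported as an SAE in any case (section 7.2.6).
- Special-interest events (section 7.2.7) include diarrhea/colitis, uveitis and interstitial pneumonia from Grade 2, and other immune-related AEs from Grade 3. They go to the sponsor within 24 hours. Under section 7.4.4, reporting to the authorities follows only if the event is also an SAE. Gastrointestinal bleeding and febrile neutropenia are not on that list.
- All AEs are collected during the reporting period, and the SAP summarizes Grade 3 or higher events separately. An event misread as non-serious within that period is lost from the SAE count but still appears in the AE data.

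**Step 5: direction and size.** The literal reading can only remove events from the SAE count, so any error is downward. SAP section 11.4.1 counts subjects and not episodes, so a subject with another SAE stays in the numerator. The number of subjects lost therefore cannot exceed the number of events lost. To go further one would need the share of SAEs that qualify through hospitalization alone, the share of those that enter as emergencies, and the share of sites that read the item literally. The documents give none of these.

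**The case against.** **The drafters probably meant emergency-room attendance.** The neighboring items are settings or reasons outside acute inpatient care, and in that company the phrase plausibly means a routine emergency visit. The preceding sentence would then still cover a subject who is kept in. This stands as a likely intention. It does not settle the text, which speaks of admission and leaves it undefined. A sponsor who intended the narrow meaning loses nothing by writing it down.

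**Other routes catch many of these events.** This also stands in part. A reader might infer that an AE with an emergency admission can never be an SAE. The documents do not support that, because the exclusion affects the hospitalization criterion alone.

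**There is no sign of under-reporting.** The version 6.0 summary records a Grade 3 upper gastrointestinal hemorrhage as an SAE. The route of admission is not given, so this does not show how the item was read. It does mean that a claim of actual under-reporting has no support.

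**The blood-products item.** A reader might infer that it also excludes admissions to transfuse treatment-related anemia, since section 5.5.4 bars prophylactic use of blood products but adds "However, these treatments are allowed for treating AEs". The text does not support this. That item falls under the second list's lead-in, which covers only stays unrelated to worsening AEs. An admission to transfuse a new or worsening AE is outside it, so the two sections do not conflict.

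**No decision depends on the SAE rate.** The primary endpoint is ORR, section 8.4.3 restricts safety to descriptive summary, and no hypothesis test uses SAE incidence. This is correct and limits the weight of the point.

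**Conclusion.** The concern holds as a defect of wording. The first list in section 7.2.3 contains an unconditional and undefined exclusion that, followed literally, contradicts the rule it qualifies. An AE leading to an emergency inpatient admission would then be an SAE only through another criterion, and sites can reasonably differ.

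The consequence is possible, not demonstrated: a downward error in the SAE count, missed 24-hour reports, and perhaps late related events that are not collected. The size cannot be estimated from the documents. Any percentage would rest wholly on assumed inputs, and none is offered here. The conclusion assumes that at least some sites apply the item as written and that no site instruction outside these two documents already clarifies it.

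The point does not touch the primary endpoint or the two-stage decision rules. It is a clarification worth making because it governs expedited reporting and costs very little.

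**What to change.** 1. Replace the item in the first list with: *emergency-room or observation visit that does not lead to inpatient admission*.
2. Add one sentence: *inpatient admission through the emergency department because of an AE meets the hospitalization criterion*.
3. Before database lock, run one reconciliation query to sites for AEs with an emergency admission that were not reported as SAEs, and reclassify and report where needed.

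The cost is a one-line change to the protocol or safety manual and a single query. Treatment, sample size and analysis methods are unchanged. The downside is that the reported SAE rate may rise. The blood-products item needs no change on this account.

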7.2.4 Progressive disease

Progressive disease is defined as the worsening of the subject's conditions caused by the indications of the study, including radiological progressions and progressions in clinical symptoms and signs. New metastases relative to the primary tumor or progressions of the previous metastases are recognized as PD. Life-threatening events, hospitalization or prolonged hospitalization, or events resulting in permanent or severe disability/incapacity/impairment of work ability, congenital anomalies or birth defects arising from the symptoms and signs of the progressive disease are not reported as SAEs. Death caused by the symptoms and signs of PD will be reported as an SAE.

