The primary efficacy endpoint was overall survival (OS). The secondary efficacy endpoints included progression-free survival (PFS), disease control rate (DCR), and objective response rate (ORR). The median overall survival in the investigational treatment group was prolonged compared with the placebo group, while the death risk was reduced by about 30%. The secondary endpoints PFS and DCR were also higher in the treatment group than those in the placebo group. Generally, no symptoms specific to advanced GC or deterioration of health-related life quality were caused. [Table 4](#). lists the primary efficacy results, and [Figure 3](#). shows the survival curves.

Endpoint	Treatment Group (n = 176)	Placebo Group (n = 91)
Overall survival (OS)		
Median (mOS, month)	6.5	4.7
HR (95% CI)	0.709 (0.537, 0.937)	
Progression-free survival (PFS)		
Median (mPFS, month)	2.6	1.8
HR (95% CI)	0.444 (0.331, 0.595)	
Objective Response Rate (CR + PR)		
2.84%	0	
Clinical Benefit Rate (CR + PR + SD)		
42.05%	8.79%	

Table 4. Efficacy results of the phase III clinical study of apatinib in GC (FAS)

[figure not shown]

Figure 3. Survival analysis of the phase III clinical study of apatinib in GC (FAS)

In the treatment group and the placebo group, the incidences of adverse drug reactions were 92.05% and 71.43%, respectively; the incidences of Grade 3/4 adverse drug reactions were 51.70% and 24.18%, respectively. Among the common adverse drug reactions (incidence $\geq 5\%$), the ones that were statistically different between the two groups in incidence included hematologic toxicities (WBC decreased, granulocytopenia, and thrombocytopenia) and non-hematologic toxicities (proteinuria, hypertension, hand-and-foot syndrome, asthenia, and hoarse voice). The incidences of serious adverse drug reactions in the investigational treatment group and the control group were 6.25% and 6.59%, respectively. The common serious adverse drug reaction was upper gastrointestinal hemorrhage in both groups.

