Headache	Grade 2 (last for ≥ 7 days) or Grade 3	Yes	Until the toxicity recovers to Grade ≤ 1	Reduce the dose by one level	Apatinib interruption for more than 28 days

In this study, the minimum dose of apatinib allowable is 250 mg/d. If the subjects still cannot tolerate the dose of 250 mg/d, apatinib should be permanently discontinued.

For subjects with gastrointestinal perforation, wound dehiscence needing clinical management, fistula, severe hemorrhage, nephrotic syndrome or hypertensive crisis, apatinib should be permanently discontinued.

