Progression-free survival (PFS): The time between the date of enrollment and the first documented tumor progression (as per RECIST 1.1 criteria, regardless of whether treatment is continued), or death due to any cause, whichever occurs first. When determining PFS, clinical exacerbations without definite evidence of progressive disease (as per RECIST 1.1) is not considered progressive disease. For subjects who die without any prior reports of progression, the date of death is considered the date of progression. Subjects without progressive disease or death will be censored on the date of their last evaluable tumor assessment. Subjects without tumor assessments during the study or death will be censored on their date of enrollment. Subjects who discontinue the treatment for reasons other than progressive disease (no subsequent tumor assessments) will be censored on their date of study discontinuation. For subjects who have not previously reported progressive disease but have initiated subsequent anti-tumor therapy, they will be censored on the date of their last evaluable tumor evaluation before starting the subsequent anti-tumor therapy, or they will be censored when starting the subsequent anti-tumor therapy. When subjects are not censored on the date of study discontinuation or the date of starting new anti-tumor treatment, the

scheduled sensitivity analysis will confirm PFS based only on the time of radiologically confirmed progression events. The occurrence of a new tumor will not be considered a progressive disease and is not censored.

Disease control rate (DCR): the proportion of subjects with a best overall response of complete response (CR), partial response (PR), or stable disease (SD) as per RECIST 1.1 criteria. If the subject achieves CR or PR, confirmation should be done at least 4 weeks (28 days) after the first evaluation. Best overall response refers to the best response assessed by the investigator, or the best response from the date of enrollment to the first documentation of progression as per RECIST 1.1 or to the start of a new anti-tumor treatment (whichever comes first). For subjects without documented progression or new anti-cancer treatment, BOR will be determined based on all response evaluations. For subjects who continue SHR-1210 treatment beyond progression, the best overall response should be based on the efficacy assessment at the time of first documented progression as per RECIST 1.1.

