### 11.5.2.3 Progression free survival (PFS)

PFS refers to the time from the start of randomization to the date of objective progressive disease or death (caused by any reason), whichever occurs first. [Table 3](#) describes progressive disease, death, or censoring.

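### Protocol 7.2.4 exempts progression-related events from SAE reporting without a rule for mixed or uncertain cause, so a serious event that 7.3.2 lists as an adverse drug reaction can miss the SAE count and the 24-hour report

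*Protocol*

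**What the plan says.** Protocol 7.2.4 defines progressive disease, for safety reporting, as worsening caused by the disease under study, "including radiological progressions and progressions in clinical symptoms and signs". It then states that life-threatening, hospitalising or disabling events "arising from the symptoms and signs of the progressive disease are not reported as SAEs". Deaths are treated differently: "Death caused by the symptoms and signs of PD will be reported as an SAE".

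Protocol 7.3.2 uses five causality categories. Four of them (definitely related, possibly related, unlikely related, indeterminable) make the event an adverse drug reaction. Only the fifth, definitely unrelated, does not.

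Protocol 7.4.3 requires an SAE to reach the authorities, the sponsor and the ethics committee within 24 hours. Protocol 7.2.7 lists the special interest events, which 7.4.4 sends to the sponsor within 24 hours: infusion reactions, immune-related events, and amylase or lipase increases. Bleeding, perforation and fistula are not named.

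The incidence and severity of SAEs is a secondary endpoint (Protocol 2.2). Safety data also enter the stage I decision to continue or stop a cohort (Protocol 8.4.2).

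**The concern.** In gastric cancer, bleeding, perforation and fistula can come from the tumour or from treatment. The protocol recognises the treatment side. Section 5.2.3 requires permanent discontinuation of apatinib in these cases: "For subjects with gastrointestinal perforation, wound dehiscence needing clinical management, fistula, severe hemorrhage, nephrotic syndrome or hypertensive crisis". It also shows that the event does not reveal its cause. Of the placebo-controlled phase III study of apatinib, section 1.1.2 says: "The common serious adverse drug reaction was upper gastrointestinal hemorrhage in both groups". Mixed or uncertain cause is therefore an ordinary situation in this trial, and apatinib is part of the regimen in both cohorts.

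For such an event 7.2.4 asks only whether it arises from progression, and 7.3.2 asks only whether a drug can be excluded. Both answers can be yes-progression and not-excluded at once, and no text says which section then governs SAE reporting. At stake are a downward bias in a secondary safety endpoint, later recognition of a bleeding or perforation signal, and different reporting of like events between sites.

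**Working it through.** There is no figure in the plan to reproduce. The check is to take one case through the rules.

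**Case.** A subject on SHR-1210 plus apatinib is hospitalised with a non-fatal gastrointestinal bleed. The investigator thinks the tumour is the main cause and rates the relation to apatinib as unlikely or indeterminable.

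| Rule | Result |
|---|---|
| AE (Protocol 7.2.2) | Yes. Worsening of an existing disease is an AE and is graded |
| Adverse drug reaction (7.3.2) | Yes. It is not definitely unrelated |
| Seriousness criterion (7.2.3) | Met, by hospitalisation |
| Progression exemption (7.2.4) | Applies on its wording. Clinical progression suffices and no relatedness threshold is set |
| SAE count and 24-hour report (7.4.3) | Can be left out |
| Special interest event (7.2.7) | No, unless the event is judged immune-related and meets the grade there |
| TEAE and Grade 3 or higher tables (SAP 11.4.1) | TEAE: yes. Grade 3 or higher: yes if so graded |

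Three variations show where the gap ends.

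1. If the bleed is fatal, it is an SAE by the express rule in 7.2.4.
2. If the investigator attributes it to apatinib and not to progression, the exemption does not apply and it is an SAE.
3. If the site reports it as an other important medical event, a criterion in 7.2.3 that the exemption does not name, it may still become an SAE. The text does not say whether that criterion or the exemption prevails.

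One further detail concerns the tables. SAP 11.4.1 counts definitely related, possibly related, indeterminable and missing causality as drug-related. It omits unlikely related. An exempted event with that rating is an adverse drug reaction under Protocol 7.3.2, but is seen only in the all-cause AE tables of the SAP.

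**What one subject is worth.** This is arithmetic on planned cohort sizes and does not estimate how often the gap occurs. If one subject's only SAE is exempted, observed SAE incidence falls by:

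- 1/19 = 5.3 percentage points in a stage I cohort
- 1/43 = 2.3 points in cohort 1 at full size
- 1/55 = 1.8 points in cohort 2 at full size

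Small counts have mattered here. The protocol's version 6.0 revision summary reports 4 apatinib-related SAEs among 11 patients, one of them an upper gastrointestinal haemorrhage, as grounds for an amendment.

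**The case against.** The strongest reply is that 7.2.4 already contains an attribution test. Progression must be caused by the study indication, and the event must arise from it. This stands: it would be wrong to say that the exemption ignores cause. What remains missing is a rule for an event with two possible causes.

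It can also be said that the event is not lost. This stands too, and it limits the point to SAE status and the 24-hour report.

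Third, attribution is not left to the investigator alone. Medical and data-management staff review the eCRF and raise queries (Protocol 12.2.2 and 12.2.3). That is a real safeguard, but it is not described as adjudication of SAE status and need not take place within 24 hours.

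Fourth, the one bleed documented in this trial was reported as an apatinib-related SAE, and bleeds on placebo in the phase III study were classed as drug reactions. Both facts suggest that investigators do not readily put bleeding down to the tumour. No passage shows a bleed being reclassified as progression.

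A reader might go further and infer a defect from the PFS definition, under which "clinical exacerbations without definite evidence of progressive disease (as per RECIST 1.1) is not considered progressive disease", and which in the SAP runs "to the date of objective progressive disease or death (caused by any reason), whichever occurs first". On that reading, a bleed put down to clinical progression counts neither as an SAE nor for PFS, and the exemption should require RECIST evidence. The documents do not support this. A non-fatal bleed is not a PFS event in any case. A broader notion of progression for safety reporting than for an imaging endpoint is not a contradiction. RECIST evidence may also be unavailable within 24 hours, since scheduled scans are 6 to 9 weeks apart.

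**Conclusion.** The gap is real and narrow. On its wording, 7.2.4 lets a non-fatal serious event that is an adverse drug reaction under 7.3.2 go unreported as an SAE when the investigator attributes it mainly to progression. The consequence is possible under-counting of a secondary safety endpoint and of the safety data used at stage I, and the loss of expedited reporting. ORR, the primary endpoint, is unaffected, and the safety analysis is descriptive.

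The frequency cannot be estimated. The documents give neither a rate of serious bleeding, perforation or fistula for these regimens nor the share that would be attributed to progression. A percentage loss would rest on assumed inputs. The conclusion assumes that sites apply 7.2.4 as written and do not use the other-important-medical-event criterion to report anyway. Exempting progression from SAE reporting is not itself at fault. The amendment is worth making because it is cheap.

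**What to change.** Reconcile Protocol 7.2.4 with 7.3.2 by stating:

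- The exemption applies only to events assessed as definitely unrelated to every study drug.
- Any event that meets a seriousness criterion and is not so assessed, including haemorrhage, perforation and fistula, is reported as an SAE whatever the progression status.
- Exempted events are recorded as such and listed separately. The listing is added to SAP 11.4.1.

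Do not make RECIST-documented progression a condition. The causality assessment does not have to wait for a scan, so the rule can work within 24 hours.

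The change concerns reporting only and alters no treatment rule. It costs a short wording amendment, one extra listing, a few more SAE forms and a slightly higher reported SAE rate, which should be noted when results are compared with trials that use a wider exemption.
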